***Data analysis:***

Summary statistics will be used to describe the clinical data and presented as mean  $\pm$  SD, median with interquartile range (IQR) or percentages as appropriate. Chi squared analysis with Fisher’s exact test (when appropriate) and Student’s t test (Mann Whiney U test for non- normal distributions) were used to compare data between the active treatment group and the placebo group with statistical significance declared for probability values of 0.05 or less.

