**Study end-points:**

***Primary end-point***

- i. Time to vasopressor independence. Defined as the time from starting the active treatment/placebo to discontinuation of all pressors
- ii. Delta SOFA score, defined as the initial SOFA score minus the day 4 SOFA score

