**Power Calculation:**

Based on the results of the preliminary study of Marik et al we project that the combination of hydrocortisone, vitamin C and thiamine could reduce time to vasopressor discontinuation from 54 (+/- 30 hours) versus 30 hours. For the additional primary outcome we projected a greater change of SOFA score of 4 (+/- 3) versus 2. Assuming a type 1 error of 5% (alpha of 0.05) and a power of 80% (the ability to detect a difference between two groups when a difference exists) would require a sample size of 94 patients. To account for dropouts and patients not requiring vasopressor therapy we will therefore aim for a sample size of 140 patients.

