***Data Collection:***

The following de-identified demographic and clinical data will be collected.

- i. Age
- ii. Sex
- iii. Weight
- iv. Admitting diagnosis and possible site of infection
- v. Blood culture results
- vi. Co-morbidities, including diabetes, hypertension, cardiac failure, COPD, malignancy
- vii. Requirement for mechanical ventilation (Y/N).
- viii. Use of vasopressor agents (Y/N). The hourly dosage of vasopressors will be recorded as the norepinephrine equivalent dosage. [70,71]
- ix. Duration of vasopressor use
- x. Time to vasopressor independence from start of active drug/placebo
- xi. Daily urine output (for first 4 days)

xii. Fluid balance after 24 and 72 hours

xiii. Presence of acute kidney injury (AKI). Presence of AKI: Acute kidney injury (AKI) will be defined using the KDIGO criteria; namely, an increase of the s-creatinine > 0.3 mg/dl or a level > 1.5 times the baseline value. [27] If the baseline s-creatinine is not known a value > 1.5 mg/dl will be regarded as diagnostic of AKI.

xiv. Length of ICU and hospital stay

xv. ICU, hospital, and 28-day mortality

xvi. Routine laboratory data for 4 days including:

a. serum creatinine

b. white cell count (WBC)

c. platelet count

d. total bilirubin

e. PaO2/FiO2 ratio

f. Procalcitonin (PCT) – on days 1 and 4

g. lactate level

h. urine oxalate level (day 4)

xvii. HostDx Sepsis genetic testing (day 1) if consent is provided for additional sub-study.

xviii. The patients' admission APACHE II and APACHE IV scores will be recorded. The APACHE IV score allows calculation of the predicted hospital mortality and predicted ICU length of stay (LOS).

ix. The daily SOFA (Sepsis-related Organ Failure Assessment) score will be recorded for the first 4 treatment days.

The APACHE II score (incrementing score of 0-71) and APACHE IV score (incrementing score 0-286) are standardized measures of disease severity that are used to predict hospital mortality and ICU LOS.

[72,73] The SOFA score was designed to sequentially assess the severity of organ dysfunction in patients who are critically ill from sepsis (incrementing score 0-24). [74]. The SOFA scores is calculated 24 hours

after admission to the ICU and daily thereafter. SOFA scores that increase by about 30 percent are associated with a mortality of at least 50 percent.[75]

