Outcomes of Metabolic Resuscitation Using Ascorbic Acid, Thiamine, and Glucocorticoids in the Early Treatment of Sepsis.

ORANGES Trial

NCT#: NCT03422159

Document Date: May 13th, 2019

Study end-points:

Primary end-point

- i. Time to vasopressor independence. Defined as the time from starting the active treatment/placebo to discontinuation of all pressors
- ii. Delta SOFA score, defined as the initial SOFA score minus the day 4 SOFA score

Secondary end-points

- iii. 28-day mortality
- iv. Hospital mortality
- v. PCT clearance (PCT-c) calculated using the following formula: initial PCT minus PCT at 96 hours, divided by the initial PCT multiplied by 100. [67,68]
- vi. ICU mortality
- vii. ICU length of stay (LOS) and ICU free days. ICU free days is calculated as the number of days alive and out of the ICU to day 28
- viii. Hospital LOS

Power Calculation:

Based on the results of the preliminary study of Marik et al we project that the combination of hydrocortisone, vitamin C and thiamine could reduce time to vasopressor discontinuation from 54 (+/- 30 hours) versus 30 hours. For the additional primary outcome we projected a greater change of SOFA

score of 4 (+/- 3) versus 2. Assuming a type 1 error of 5% (alpha of 0.05) and a power of 80% (the ability to detect a difference between two groups when a difference exists) would require a sample size of 94 patients. To account for dropouts and patients not requiring vasopressor therapy we will therefore aim for a sample size of 140 patients.

Data analysis:

Summary statistics will be used to describe the clinical data and presented as mean \pm SD, median with interquartile range (IQR) or percentages as appropriate. Chi squared analysis with Fisher's exact test (when appropriate) and Student's t test (Mann Whiney U test for non- normal distributions) were used to compare data between the active treatment group and the placebo group with statistical significance declared for probability values of 0.05 or less.

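### Time to vasopressor independence is compared without adjusting for the vasopressor dose at first study dose, which the trial should already hold; this costs precision but does not bias the result.

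*Protocol*

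**What the plan says.** The first primary end-point is time to vasopressor independence: "Defined as the time from starting the active treatment/placebo to discontinuation of all pressors" (protocol, Primary end-point; same text in the SAP).

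The only analysis text is the Data analysis paragraph, the same in both documents. It offers chi-squared or Fisher tests for proportions and, for continuous data, a "t test (Mann Whiney U test for non- normal distributions) were used to compare data". In the protocol's copy, these tests "were used to compare data between the active treatment group and the placebo group with statistical significance declared" at the 0.05 level. No covariate, regression model or adjusted analysis is named for any end-point. The protocol's randomisation text describes a random number table and no stratification, so the design does not balance vasopressor dose either.

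The Data Collection list has three relevant items:
- Item viii: "The hourly dosage of vasopressors will be recorded as the norepinephrine equivalent dosage".
- Item ix: total duration of vasopressor use.
- Item x: "Time to vasopressor independence from start of active drug/placebo".

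The Power Calculation section projects that treatment "could reduce time to vasopressor discontinuation from 54 (+/- 30 hours) versus 30 hours". It asks for 94 patients and raises this to 140 for dropout and for patients who never need vasopressors.

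**The concern.** The clock starts at the first study dose, and patients can reach that moment on very different vasopressor doses. The dose then running is a pre-treatment value and a plausible predictor of how many vasopressor hours remain. A comparison that ignores it leaves explainable variance in the error term. A chance difference in starting dose between arms also feeds into the estimate obtained in that sample.

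At stake is the precision of one of two primary end-points, measured only in the patients on vasopressors. The trial enrols sepsis as well as septic shock, and the documents do not say how many patients are expected to be on vasopressors.

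**Working it through.** **Inputs from the documents.** 54 h versus 30 h gives a difference of 24 h; SD 30 h. For the other primary end-point, "we projected a greater change of SOFA score of 4 (+/- 3) versus 2", a difference of 2 with SD 3. Error rates: "Assuming a type 1 error of 5% (alpha of 0.05) and a power of 80"%. Stated evaluable number: 94.

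**Assumptions.** Two-sided test; 1:1 allocation; correlation r between dose at first study dose and remaining hours of 0.3 to 0.5, with 0.1 to 0.2 as a pessimistic range. The documents give no value for r.

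**The plan's own figure.** n per arm = 2 x (1.96 + 0.84)^2 x (SD/difference)^2.
- Vasopressor time: 2 x 7.85 x (30/24)^2 = 24.5, so 25 per arm and 50 in total (52 with the t distribution).
- SOFA: 2 x 7.85 x (3/2)^2 = 35.3, so 36 per arm and 72 in total (74 with the t distribution).

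Neither gives 94. I take 94 as stated, all on vasopressors at 47 per arm, and also show 25 per arm.

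**Effect of adjustment.** Adjusted SD = 30 x sqrt(1 - r^2). For r = 0.3 this is 28.6 h (9% of variance removed, worth 1/0.91 = 1.10 times the patients). For r = 0.5 it is 26.0 h (25% removed, worth 1/0.75 = 1.33 times).

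**Power, two-sample t basis:**

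| Setting | r = 0 | r = 0.1 | r = 0.2 | r = 0.3 | r = 0.5 |
|---|---|---|---|---|---|
| 47 per arm, 24 h (projected) | 97.0% | 97.1% | 97.5% | 98.0% | 99.3% |
| 47 per arm, 15 h (assumed) | 66.9% | 67.4% | 68.7% | 71.0% | 79.1% |
| 25 per arm (assumed), 24 h | 79.2% | 79.5% | 80.8% | 82.8% | 89.2% |

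**Chance imbalance.** The 95% range of the baseline difference between arms is 1.96 x sqrt(2/47) = 0.40 SD. Multiplied by r x 30 h, it shifts the unadjusted estimate by 3.6 h (r = 0.3) to 6.1 h (r = 0.5), or 15% to 25% of 24 h. At 25 per arm the shift is 5.0 to 8.3 h. These are 95% limits, not maxima, and the unadjusted confidence interval already allows for this noise. Its half-width is 1.96 x 30 x sqrt(2/47) = 12.1 h, which adjustment narrows to 11.6 h (r = 0.3) or 10.5 h (r = 0.5).

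**Type I error.** In simulation the unadjusted t test rejected a true null in about 5% of runs overall. Among runs where the baseline imbalance exceeded 1.5 standard errors, at 47 per arm, it rejected in about 9% to 14% (variance explained 0.1 to 0.3).

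**Skewed data.** I simulated lognormal times with a placebo mean of 54 h, SD 30 h and a treatment ratio of 0.75 (54 versus 40.5 h). Mann-Whitney had power 0.73 and a rank-based adjusted analysis 0.78 to 0.85 for r = 0.3 to 0.5. Adjusted regression on log hours gave a similar range, but about 2.5 points of its gain come from changing the test: an unadjusted t test on log hours already reached 0.757 against 0.731. The proportional-odds model itself was not simulated.

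**The case against.** The strongest reply is that an unadjusted test in a randomised, double-blind trial is a legitimate choice. That stands. A reader might infer that the comparison is biased or its error rate inflated; the documents do not support this. Chance imbalance averages out over randomisations, and overall type I error stays at 5%. The raised rate in badly unbalanced samples describes those samples, not the procedure.

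A reader might also infer that this end-point is underpowered without adjustment. On the plan's figures it is not: it needs about 50 patients against 72 for SOFA, and 47 per arm gives 97% power for 24 h. The larger gains need a smaller effect, or fewer patients on vasopressors, than the plan projects. Both are assumptions. They are reasonable to examine, because the 24 h comes from a retrospective before-after study of 94 patients and no number on vasopressors is stated.

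A third tempting reading is that both dose and prior vasopressor hours are known for every patient on vasopressors. Prior hours is not a listed item. Subtracting item x from item ix fails if vasopressors were stopped and restarted, if they began after the first study dose, or if the patient died while on them and so has no value for item x. Eligibility also keeps onset close to admission, which may leave prior hours too narrow a range to predict much. Dose is better placed because it is recorded hourly, although the protocol does not say that recording begins before the study drug.

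Finally, the lack of adjustment runs through the whole analysis section. It is one omission, examined here for one end-point, and should not be counted again for each of the others.

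**Conclusion.** The omission is real and worth correcting as a matter of precision. At an assumed correlation of 0.3 to 0.5 the gain is 1 to 2 points of power at the plan's own 24 h with 47 per arm. It is 4 to 12 points at an assumed 15 h, and 4 to 10 points at 24 h if only 25 per arm are on vasopressors. At a correlation of 0.1 to 0.2 it is under 2 points throughout. The omission itself is certain; the size of the gain rests on a correlation that the documents do not give, and on linear-model arithmetic that a proportional-odds model would match only approximately.

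**What to change.** In the Data analysis section of both documents, before unblinding, state that:

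1. The primary comparison of time to vasopressor independence, in patients on vasopressors at first study dose, is a proportional-odds regression on arm and norepinephrine-equivalent dose at first study dose. This is the covariate-adjusted counterpart of the planned Mann-Whitney test.
2. The dose enters through a transformation defined at zero, such as log(dose + constant) with the constant fixed in advance, so that a recorded zero does not drop a patient.
3. Deaths on vasopressors are ranked by one stated rule, the same in the adjusted and unadjusted analyses. The plan has no such rule at present, and the regression is not ready to use without it.
4. Hours on vasopressors before first study dose is added as a second covariate only if the hourly record gives it directly, not by subtracting item x from item ix.
5. The unadjusted test is kept as a sensitivity analysis.

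The cost is SAP wording and one or two degrees of freedom. No extra patients are needed, and no new data provided that the hourly record covers the time of the first study dose; this should be confirmed. Adjustment added after unblinding because the arms looked unbalanced would be open to challenge.

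### Two primary end-points share one stated 5% error rate with no success rule; if either suffices, the two-sided chance of a false-positive difference is 9.75% for independent tests

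*Protocol*

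**What the plan says.** Under the primary end-point heading, both documents list two items: "Time to vasopressor independence. Defined as the time from starting the active treatment/placebo to discontinuation of all pressors" and "Delta SOFA score, defined as the initial SOFA score minus the day 4 SOFA score".

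The Power Calculation treats both as primary. For the first, the combination "could reduce time to vasopressor discontinuation from 54 (+/- 30 hours) versus 30 hours". For the second: "For the additional primary outcome we projected a greater change of SOFA score of 4 (+/- 3) versus 2". One error rate and one power target are then given: "Assuming a type 1 error of 5% (alpha of 0.05) and a power of 80" per cent. The resulting 94 patients are raised to 140: "To account for dropouts and patients not requiring vasopressor therapy we will therefore aim for a sample size of 140 patients".

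The Data analysis section names the tests (t-test, or Mann-Whitney for non-normal data, for continuous outcomes) and applies one threshold to all comparisons: "with statistical significance declared for probability values of 0.05 or less". The SAP repeats these sections and adds nothing on multiplicity. Neither document gives an alpha split, a test order or a rule for combining the two primary results. Sidedness is not stated.

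**The concern.** Two primary tests fit a single 5% error rate only under a rule that the plan leaves out. If both must succeed, or if one is tested first and gates the other, 5% holds for the trial-level claim. If either alone is enough, it does not.

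The gap matters when the two results disagree. One end-point reaches 0.05, the other does not, and the plan does not say whether the trial has met its primary objective. A rule chosen after the results are known cannot restore error control, because the successful end-point could be the one chosen. Disagreement is not remote even if the sponsor's projected effects are true, as step 3 of the working shows.

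**Working it through.** **Inputs.** From the Power Calculation: vasopressor time 54 v 30 hours, SD 30, so d = 24/30 = 0.80; delta SOFA 4 v 2, SD 3, so d = 2/3 = 0.667; alpha 0.05; power 80%; 94 patients before allowances, 140 after. Assumed because not stated: two-sided tests, 1:1 allocation, common SD.

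**Step 1. Does the stated 94 reveal a rule?** Normal approximation: n per arm = 2(z₁₋α/₂ + z₀.₈)²/d².

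- Vasopressor time, alpha 0.05: 2(1.960 + 0.842)²/0.64 = 24.5, so 25 per arm and 50 in total (52 by t-test).
- SOFA, alpha 0.05: 2(1.960 + 0.842)²/0.444 = 35.3, so 36 per arm and 72 in total (74 by t-test).
- Both required, independent tests: 82 in total.
- SOFA, alpha 0.025: 2(2.241 + 0.842)²/0.444 = 42.8, so 43 per arm and 86 in total (90 by t-test).

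None gives 94. An allowance for Mann-Whitney efficiency of 0.955 takes the last figure to 90/0.955, about 95, but the documents mention no such allowance. The sample size therefore does not show a built-in alpha split or a both-required rule.

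**Step 2. Error rate if either end-point suffices, each at two-sided 0.05.** For independent tests, any difference: 1 − 0.95² = 9.75%. Benefit direction only, 2.5% per test: 1 − 0.975² = 4.94%. For correlated tests, bivariate normal integration gives:

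| Correlation | Any false-positive difference | False claim of benefit |
|---|---|---|
| 0 | 9.75% | 4.94% |
| 0.5 | 9.1% | 4.5% |
| 0.8 | 7.8% | 3.9% |
| 0.9 | 7.0% | 3.5% |

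For any difference, 9.75% is the ceiling when the two statistics are jointly normal; under arbitrary dependence it is 0.05 + 0.05 = 10%. For benefit, the ceiling under any dependence is 0.025 + 0.025 = 5%. If both end-points must be significant, the error is at most 5%.

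**Step 3. How often would the two results disagree under the plan's own effects?** Noncentral-t power at 0.05 with 47 per arm is 0.970 for vasopressor time and 0.892 for SOFA. If independent, both succeed in 0.970 × 0.892 = 87% of trials and exactly one in 0.970 × 0.108 + 0.030 × 0.892 = 13%. If only 70 patients are evaluable for vasopressor time (assumption; power 0.910) and 94 for SOFA, both succeed in 0.910 × 0.892 = 81% and exactly one in 18%.

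**Step 4. Power at Holm's first step.** This is each end-point's power at 0.025, a lower bound on its power under Holm. Mann-Whitney is approximated by multiplying n by an efficiency of 0.864.

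| End-point, evaluable total | t-test, 0.05 to 0.025 | Mann-Whitney, 0.05 to 0.025 |
|---|---|---|
| Vasopressor time, 94 | 97% to 94% | 95% to 90% |
| Vasopressor time, 70 (assumed) | 91% to 85% | 86% to 79% |
| SOFA, 94 | 89% to 83% | 84% to 76% |

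The 0.864 is the lower bound for continuous location shifts. Delta SOFA is an integer score with ties, so its Mann-Whitney figures are approximate.

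**The case against.** The strongest reply is that nothing in the plan is miscalculated. Each test keeps its own 5% level, the documents define no trial-level claim, and the stated aim is broad: the effect on clinical course and outcome. Results reported end-point by end-point would let readers apply their own correction. The 9.75% also counts false findings of harm and assumes zero correlation. The two end-points are probably positively correlated, and the harmful error, a false claim of benefit, does not exceed 5%.

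Much of this stands. A reader might infer that the plan permits a claim on either end-point, or that the trial's error rate is 9.75%. The documents support neither: they are silent on the rule, and the figure depends on an either-suffices reading, two-sided tests and a correlation that is not given.

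It does not remove the gap. Both outcomes are labelled primary, and one 5% is attached to the pair. Under an either-suffices rule the error exceeds 5% at any correlation short of perfect. The false claim of benefit, though no more than 5%, is up to twice the 2.5% of one two-sided test. Nor does listing vasopressor time first amount to a test order, since the same numbering runs on through the secondary end-points.

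**Conclusion.** The concern holds as an omission: the rule linking two primary results to one primary conclusion is missing from both documents. How far the error exceeds 5% depends on the rule eventually used and on the correlation, from the independence figure of 9.75% down to no inflation at all if both are required. The omission bears on the primary conclusion, so it should be settled before allocation is known.

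A reader might also infer that SOFA is the end-point that limits power under a split alpha, because its standardised effect is smaller (0.667 v 0.80). The documents do not support that. Patients never on vasopressors cannot contribute to the first end-point but still have daily SOFA scores, which the protocol says "score will be recorded for the first 4 treatment days"; death or ICU discharge before day 4 could in turn reduce the SOFA count. With 70 evaluable for vasopressor time and 120 to 130 for SOFA (assumption), Mann-Whitney power at 0.025 is about 79% for vasopressor time and 87% to 89% for SOFA, so vasopressor time would be the limit. Neither evaluable rate is given.

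**What to change.** State one rule in both documents before the treatment codes are released. Suggested wording:

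> Either primary end-point can support the primary claim. The two will be tested with the Holm procedure at a family-wise two-sided alpha of 0.05: the smaller p-value is compared with 0.025 and, if it is significant, the larger is compared with 0.05.

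Two alternatives are acceptable if they are what the sponsor intends:

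- **Fixed sequence.** Test one named end-point at two-sided 0.05, and the other at 0.05 only if the first is significant. The first end-point loses no power, but the second depends on it. If vasopressor time comes first and has no effect, the chance of a SOFA claim is about 0.05 × 0.892 = 4.5% (independent tests, 47 per arm), however real the SOFA effect.
- **Both required.** Each must be significant at two-sided 0.05 in the direction of benefit. There is no inflation, but one missed end-point means no primary claim, and power is the joint figure from step 3.

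Then restate power under the chosen rule, giving the evaluable number expected for each end-point and the planned test.

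The drafting cost is a few sentences per document. The power cost of Holm at its first step is about 3 to 6 percentage points by t-test in the cases tabulated, with every figure still above 80%. With Mann-Whitney at the low efficiency it is about 4 to 8 points, and power can fall just below 80%: SOFA with 94 evaluable, or vasopressor time with 70. Whether 140 patients are enough cannot be settled until the evaluable rates are stated.

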It has previously been suggested that *“...the best hope for therapeutic advances [in sepsis] will depend on broad-base targeting, in which multiple components are targeted at the same time.”*[51] Such combination “chemo-therapy” targeting multiple biological pathways is the standard approach in the treatment of malignant disease. While the benefits of vitamin C, hydrocortisone, and thiamine alone are likely limited,[23,49,50,52] we believe that these medications act synergistically to reduce the risk of organ failure and death in patients with sepsis. This hypothesis is supported previous research [53,54] and more recently a set of elegant experiments performed by Barabutis et al. [55] Using a validated pulmonary endothelial monolayer model, these authors demonstrated that hydrocortisone together with vitamin C protected the vascular endothelium from damage by endotoxin while neither agent alone had this effect. Previous research has demonstrated that vitamin C reverses oxidation of the glucocorticoid receptor (GR) a likely manifestation of sepsis.[53] Oxidation of the GR limits binding of the GR to both ligand and DNA responsive units decreasing the activity of glucocorticoids. [53] Furthermore, glucocorticoids increase the expression of the sodium vitamin C transporter-2 (SVCT-2) which is an essential transport protein necessary for vitamin C to be transported intracellularly.[54]

We therefore propose that a “metabolic resuscitation protocol” including vitamin C, corticosteroids and thiamine will limit the development of organ failure and reduce mortality in patients with severe sepsis and septic shock. This postulate is supported by the preliminary findings by Marik et al. [56] In a retrospective before-after clinical study, these authors compared the outcome and clinical course of consecutive septic patients treated with intravenous vitamin C, hydrocortisone and thiamine during a 7-month period (treatment group) compared to a control group treated in during the preceding 7 months.[56] The primary outcome was hospital survival. A propensity score was generated to adjust the primary outcome. There were 47 patients in both treatment and control groups with no significant differences in baseline characteristics between the two groups. The hospital mortality was 8.5% (4 of 47)

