***Secondary end-points***

- iii. 28-day mortality
- iv. Hospital mortality
- v. PCT clearance (PCT-c) calculated using the following formula: initial PCT minus PCT at 96 hours, divided by the initial PCT multiplied by 100. [67,68]
- vi. ICU mortality
- vii. ICU length of stay (LOS) and ICU free days. ICU free days is calculated as the number of days alive and out of the ICU to day 28
- viii. Hospital LOS

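### Seven secondary comparisons, three of them overlapping mortality measures, may each be declared significant at 0.05 with no order, adjustment or exploratory label

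*Protocol*

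**What the plan says.** The protocol's Data analysis section names the tests (chi-squared or Fisher's exact; Student's t or Mann-Whitney) and says that they "were used to compare data between the active treatment group and the placebo group", "with statistical significance declared for probability values of 0.05 or less". The SAP repeats the rule: "compare data between the active treatment group and the placebo group with statistical significance declared for probability values of 0.05 or less". Neither text separates primary from secondary end-points when it sets this threshold.

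The secondary list, the same in both documents, has six items, iii to viii. Three are mortality: "28-day mortality", "Hospital mortality" and "ICU mortality". Item vii, "ICU length of stay (LOS) and ICU free days", holds two variables. With PCT clearance and hospital length of stay, that makes seven comparisons. Neither document orders them, adjusts for their number, ties them to the primary result or calls them exploratory.

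The protocol's Background proposes that the treatment "will limit the development of organ failure and reduce mortality in patients with severe sepsis and septic shock". It does not say which mortality measure would bear on that proposal.

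**The concern.** Read as written, the rule treats a secondary p-value of 0.05 exactly like a primary one. Seven chances at 5% do not add up to a 5% risk of a false statement, and no text tells the reader to discount an isolated result.

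Mortality is where this matters most. It is part of the proposal in the Background, and a declared mortality difference would be the most consequential sentence the trial could publish. It is measured in three ways with none marked as the main one. The cited literature does not settle the choice: the before-after study behind the trial reports hospital mortality (8.5% against 40.4%), while the cited vitamin C trial in septic shock reports 28-day mortality (14% against 64%). If, say, ICU mortality gave p = 0.04 and 28-day mortality p = 0.12, the plan would not say which one to interpret.

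**Working it through.** **The plan's own figure.** There is none to reproduce. The Power Calculation sets a type 1 error of 5%, but neither document states an error rate for the secondary family.

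**Inputs from the documents.** Threshold 0.05; seven secondary comparisons; three mortality measures; total sample size 140.

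**Inputs that must be assumed.** Two-sided tests; 1:1 allocation with no losses, so 140 / 2 = 70 per arm; the correlations between tests; the death rates. All rates below suppose no treatment effect on any secondary end-point.

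**Step 1: seven tests without correlation.**

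- Independent tests: 1 - (1 - 0.05)^7 = 1 - 0.698 = 0.302, or 30%.
- Upper bound under any dependence: 7 × 0.05 = 0.35, or 35%.

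**Step 2: allow for overlap.** The end-points are linked; ICU-free days, for example, depends on survival and on ICU stay. Simulated correlated normal test statistics, each tested two-sided at 0.05, gave:

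| Correlation pattern | At least one of seven significant |
|---|---|
| All pairs 0.3 | 27.2% |
| All pairs 0.5 | 23.0% |
| All pairs 0.7 | 17.9% |
| All pairs 0.9 | 11.4% |
| Mortality tests 0.5, others independent | 28.8% |
| Mortality tests 0.9, others independent | 25.4% |

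Two patient-level null models, with 70 per arm, overlapping mortality and linked length-of-stay variables, gave 20.6% to 23.1% when mortality was tested by chi-squared (uncorrected) or its normal equivalent. One of them gave 18.9% with Fisher's test. Both rest on assumed distributions, so they show what is plausible and do not estimate this trial's rate.

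**Step 3: the three mortality measures alone.**

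- Independent: 1 - 0.95^3 = 1 - 0.857 = 0.143, or 14%.
- With realistic overlap (hospital mortality 20% to 40%, 70% of in-hospital deaths in the ICU, 70 per arm), at least one chi-squared test was significant in 9% to 10% of simulated null trials.
- With Fisher's test at 25% hospital mortality, the rate was 6.1%. A single Fisher test at this size has a true two-sided error of only about 3%, so a choice of three measures still roughly doubles it.
- Counting only results in favour of treatment, the chi-squared rate was 4.5% to 5.1%, against 0.05 / 2 = 2.5% for one test.
- In one run, which also assumed 90% of hospital deaths by day 28 and 3% of hospital survivors dying by day 28, about 87% of the trials with a false mortality result had measures that disagreed: at least one significant, but not all three.

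**The case against.** The strongest reply is that the plan does rank its end-points. It labels them primary and secondary and bases the sample size only on the primaries. The threshold is a generic sentence about comparing data. It does not define trial success, and a careful reader will discount one small p-value among seven. Mortality appears as a hypothesis only in the Background; the Specific Aims speak of clinical course and outcome.

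Much of this stands, and it rules out three stronger readings.

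- A reader might infer that the plan offers secondary significance as a route to success when both primaries fail. The documents do not say that. They define no success rule; the gap is that the threshold does not exclude such a declaration.
- A reader might take 23% as the false-positive rate. It needs an assumed common correlation of 0.5, and the documents give none.
- A reader might apply the 23% or 30% to mortality. Those rates belong to all seven comparisons, including PCT clearance and the length-of-stay variables. The mortality-only rate is about 10% or less, and about 5% in the direction of benefit.

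What the reply does not remove is the wording. The label 'secondary' does not make a result descriptive when the same sentence declares significance for primary and secondary comparisons alike.

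**Conclusion.** The point holds as a defect in what the plan permits to be declared. It does not affect the data, the patients or the primary estimates. If no secondary end-point is affected by treatment, the chance of at least one false declaration among the seven is 30% under independence and lower with overlap: about 23% at an assumed correlation of 0.5 and 11% at 0.9. For the three mortality measures it is about 10% with chi-squared and about 6% with Fisher's test, given the assumed death rates and 70 per arm, with about half in the direction of benefit. The count of seven, the shared threshold and the missing order or label come straight from the documents; every correlation and death rate is an assumption. Because the remedy is cheap and changes what the trial may conclude, it should be made, but it is a modest improvement.

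**What to change.** In the Data analysis text of both documents:

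1. Limit declarations of statistical significance to the primary end-points.
2. State that all secondary end-points are exploratory and will be reported as effect estimates with unadjusted 95% confidence intervals and nominal p-values, with no declaration of significance.
3. Name, before unblinding, the one mortality measure that is the main one for interpretation. 28-day mortality is a reasonable choice because its horizon is fixed; the other two then support it. If it is chosen, add a line on how vital status is obtained after discharge, which the documents do not describe.

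Formal testing of one key secondary, conditional on the primary result, is optional. It cannot be written yet, because the plan lists two primary end-points and does not say whether success needs one or both. That would have to be defined first.

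The cost is a few sentences, with no added patients; 28-day mortality is already on the data collection list. The downside is that an isolated p-value of 0.05 or less on a secondary end-point, mortality included, could no longer be called significant.
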